1. AMENDMENTS FROM PREVIOUS VERSION(S)

None.

2. INTRODUCTION

The primary purpose of this non-randomized, open-label study is to characterize the effect of varying degrees of hepatic impairment on the plasma pharmacokinetics (PK) of PF-06865571 following administration of a single, oral, 100 mg dose of PF-06865571. NAFLD/NASH is associated with varying degrees of hepatic impairment. Recognizing that the target population of PF-06865571 is patients with NAFLD/NASH and that the major clearance mechanism of PF-06865571 is metabolism in the liver, the current study is proposed to evaluate whether there is any clinically meaningful effect of hepatic impairment on the plasma PK of PF-06865571.

2.1. Study Design

This is a Phase 1, non-randomized, open-label, single-dose, parallel-cohort, multicenter study to compare the pharmacokinetics of PF-06865571 in adult participants with varying degrees of hepatic impairment relative to participants without hepatic impairment after a single, oral 100 mg dose administered in the fed state. A total of approximately 24 participants with varying degrees of hepatic function will be dosed in the study as shown in Table 2.

Table 2. Hepatic Function Categories Based on Child Pugh Scor	Table 2. H	epatic Fur	action Cate	gories Base	ed on Child	Pugh Score
---	------------	------------	-------------	-------------	-------------	------------

Cohort	Description	Child-Pugh Score	Number of Subjects
1	Without hepatic impairment	Not Applicable	6^a
2	Mild hepatic impairment	Class A (5 to 6 points)	6
3	Moderate hepatic impairment	Class B (7 to 9 points)	6
4	Severe hepatic impairment	Class C (10 to 15 points)	6^b

a. Additional participants may be dosed to a maximum of 8 participants to ensure mean age ± 5 years and mean body weight ± 10 kg of this cohort is aligned with the pooled average assessed when $\geq 75\%$ of participants are dosed across the other 3 cohorts.

[figure not shown]
Categorization of participants into Cohort 2-4, inclusive, will be done based on Child-Pugh scores determined at the Screening visit. Participants will be dosed in a staged manner such that those with moderate and severe hepatic impairment (Cohorts 3 and 4) will be evaluated first. Dosing in participants with mild hepatic impairment (Cohort 2) will initiate when approximately 50% of the total participants in Cohorts 3 and 4 have been dosed. Participants without hepatic impairment (Cohort 1) will be recruited near the end of the study to match the average demographics (at a minimum, age and weight; and gender as much as practically possible) across the pooled Cohorts 2 through 4.

b. If recruitment across the sites selected proves to be prohibitive, study will dose only 4 participants in this cohort.

Participants who prematurely discontinue for non-safety related reasons may be replaced, at the discretion of the principal investigator (PI) and sponsor study team.

The overall study design is summarized in Figure 1. For individual participants, the total duration of participation from the Screening visit to the follow-up visit will range from 5 weeks (minimum) to 9 weeks (maximum).

Figure 1. Study Design

2.2. Study Objectives

Objectives	Endpoints	
Primary:	Primary:	
• To compare the PK of PF-06865571 following administration of a single oral dose in adult participants with varying degrees of hepatic impairment relative to ageand body weight-matched participants without hepatic impairment.	• PF-06865571 PK parameters derived from plasma: C_{max} AUC _{last} , and AUC _{inf} .	

Secondary:	Secondary:
• To evaluate the safety and tolerability of a single oral dose of PF-06865571 when administered to adult participants with varying degrees of hepatic impairment relative to ageand body weight-matched participants without hepatic impairment.	Assessment of treatment-emergent adverse events, clinical laboratory tests, vital signs, and 12-lead ECGs
CCI	

3. INTERIM ANALYSES, FINAL ANALYSES AND UNBLINDING

No formal interim analysis will be conducted for this study. As this is an open-label study, the sponsor may conduct unblinded reviews of the data during the course of the study for the purpose of safety assessment, facilitating PK modeling, and/or supporting further clinical development.

4. HYPOTHESES AND DECISION RULES

4.1. Statistical Hypotheses

There is no statistical hypothesis testing planned for this study.

4.2. Statistical Decision Rules

No statistical decision rules are applied.

5. ANALYSIS SETS

5.1. Pharmacokinetic (PK) Analysis Set

5.1.1. Concentration Analysis Set

The PK concentration population will be defined as all participants who received PF-06865571 and in whom at least 1 plasma concentration value is reported.

5.1.2. Parameter Analysis Set

The PK parameter analysis population is defined as all participants dosed who have at least 1 of the PK parameters outlined in Section 6.3.1.

5.2. Pharmacodynamic Analysis Set

None.

5.3. Safety Analysis Set

All participants who receive at least 1 dose of investigational product will be included in the safety analyses and listings.

5.4. Other Analysis Sets

None.

5.5. Treatment Misallocations

All analyses will be performed on an "as-treated" basis and will not include data from participants who are not treated.

5.6. Protocol Deviations

Participants who experience events that may affect their PK profile (e.g. lack of compliance with dosing) may be excluded from the PK analysis. At the discretion of the pharmacokinetist a concentration value may also be excluded if the deviation in sampling time is of sufficient concern or if the concentration is anomalous for any other reason.

A full list of protocol deviations will be compiled and reviewed to identify major and minor deviations prior to database closure.

5.6.1. Deviations Assessed Prior to Dosing

At Screening, the investigator will assess participants against the inclusion and exclusion criteria as set out in Sections 5.1 and 5.2 of the protocol.

5.6.2. Deviations Assessed Post-Dosing

A full list of protocol deviations for the study report will be compiled prior to database closure; only important protocol deviations will be reported in the Clinical Study Report (CSR). Any significant deviation from the protocol will be reviewed prior to database closure and a decision taken regarding evaluation for each analysis population.

6. ENDPOINTS AND COVARIATES

6.1. Efficacy Endpoint(s)

None.

6.2. Safety Endpoints

The following data are considered in standard safety summaries (see protocol for collection days and list of parameters):

- adverse events,
- laboratory data,
- vital signs data,
- ECG results.

All events that start on or after the first dosing day and time and during the active collection period as specified in the protocol will be counted as treatment emergent adverse event (TEAE). Events that occur in a non-treatment period (for example, Follow-up) will be counted as treatment emergent and attributed to the treatment taken. For the safety endpoints Day 1 planned predose measurements will serve as baseline.

6.3. Other Endpoints

6.3.1. PK Endpoints

Blood samples for PK analysis of PF-06865571 will be taken according to the Schedule of Activities given in the protocol. The following PK parameters will be calculated for PF-06865571 (if possible) from the concentration-time data using standard noncompartmental methods:

PK Parameter	Analysis Scale	PF-06865571	Definition	
AUC _{inf} *	ln		Area under the plasma concentration-time	
		A, D	profile from time zero to the time of the last	
			quantifiable concentration (C _{last})	
AUC _{last}	ln		Area under the plasma concentration-time	
		A, D	profile from time zero extrapolated to	
			infinite time	
C_{max}	ln	A, D	Maximum plasma concentration	
CCI				

Key: A=analyzed using statistical model, D=displayed with descriptive statistics, ln=natural-log transformed, R=raw (untransformed), *=if data permits

6.3.2. PD Endpoints

None.

6.4. Covariates

No covariate for primary analysis (i.e. ANOVA) will be included in the model.

CC

7. HANDLING OF MISSING VALUES

The handling of missing values for PK data is described in this section. For the analysis of safety endpoints, the sponsor data standard rules for imputation will be applied.

7.1. Concentrations Below the Limit of Quantification

In all data presentations (except listings), concentrations below the limit of quantification (BLQ) will be set to zero. In listings BLQ values will be reported as "<LLQ", where LLQ will be replaced with the value for the lower limit of quantification.

7.2. Deviations, Missing Concentrations and Anomalous Values

In summary tables and plots of median profiles, statistics will be calculated having set concentrations to missing if 1 of the following cases is true:

- 1. A concentration has been collected as ND (i.e. not done) or NS (i.e. no sample),
- 2. A deviation in sampling time is of sufficient concern or a concentration has been flagged anomalous by the pharmacokinetist.

Note that summary statistics will not be presented at a particular time point if more than 50% of the data are missing.

7.3. Pharmacokinetic Parameters

Actual PK sampling times will be used in the derivation of PK parameters.

If a PK parameter cannot be derived from a participant's concentration data, the parameter will be coded as NC (i.e. not calculated). (Note that NC values will not be generated beyond the day that a participant discontinues.)

In summary tables, statistics will be calculated by setting NC values to missing; and statistics will be presented for a particular hepatic function group with ≥ 3 evaluable measurements. For statistical analyses (i.e. analysis of variance), PK parameters coded as NC will also be set

to missing; and analyses will not be performed for a particular parameter if more than 50% of the data are NC.

If an individual participant has a known biased estimate of a PK parameter (due for example to an unexpected event such as vomiting before all the compound is adequately absorbed in the body), this will be footnoted in summary tables and will not be included in the calculation of summary statistics or statistical analyses.

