4. STUDY DESIGN

4.1. Overall Design

This is a Phase 1, non-randomized, open-label, single-dose, parallel-cohort, multicenter study to compare the pharmacokinetics of PF-06865571 in adult participants with varying degrees of hepatic impairment relative to participants without hepatic impairment after a single, oral 100 mg dose administered in the fed state. A total of approximately 24 participants with varying degrees of hepatic function will be dosed in the study as shown in [Table 1](#).

Table 1. Hepatic Function Categories Based on Child Pugh Score

Cohort	Description	Child-Pugh Score	Number of Subjects
1	Without hepatic impairment	Not Applicable	6a
2	Mild hepatic impairment	Class A (5 to 6 points)	6
3	Moderate hepatic impairment	Class B (7 to 9 points)	6
4	Severe hepatic impairment	Class C (10 to 15 points)	6b

[figure not shown]
- a. Additional participants may be dosed to a maximum of 8 participants to ensure mean age ± 5 years and mean body weight ± 10 kg of this cohort is aligned with the pooled average assessed when $\geq 75\%$ of participants are dosed across the other 3 cohorts.
- b. If recruitment across the sites selected proves to be prohibitive, study will dose only 4 participants in this cohort.

Categorization of participants into Cohort 2-4, inclusive, will be done based on Child-Pugh scores determined, as described in [Appendix 8](#), at the Screening visit. Participants will be dosed in a staged manner such that those with moderate and severe hepatic impairment (Cohorts 3 and 4) will be evaluated first. Dosing in participants with mild hepatic impairment (Cohort 2) will initiate when approximately 50% of the total participants in Cohorts 3 and 4 have been dosed. Participants without hepatic impairment (Cohort 1) will be recruited near the end of the study to match the average demographics (at a minimum, age and weight; and gender as much as practically possible) across the pooled Cohorts 2 through 4. **Approval from the sponsor must be obtained before proceeding with recruitment for participants in Cohort 1 or Cohort 2.**

Participants who prematurely discontinue for non-safety related reasons may be replaced, at the discretion of the principal investigator (PI) and sponsor study team.

The overall study design is summarized in [Figure 1](#). For individual participants, the total duration of participation from the Screening visit to the follow-up visit will range from 5 weeks (minimum) to 9 weeks (maximum).

Figure 1. Study Design

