4.2. Scientific Rationale for Study Design

This study involves participants with varying degrees of hepatic impairment and participants without hepatic impairment, matched for age as well as body weight (and gender as much as practically possible). A single dose of PF-06865571 is proposed since single dose plasma PK is generally predictive of exposure upon repeated dosing, especially given that the observed relatively short terminal half-life ($t_{1/2}$) of PF-06865571 resulted in minimal accumulation upon repeated dosing of both Q8H and Q12H frequency.

CCI [REDACTED]

[REDACTED] serial PK samples will be collected over 48 hours in participants without hepatic impairment (Cohort 1). CCI [REDACTED]

[REDACTED] serial PK samples will be collected over 72 hours postdose to adequately characterize the elimination phase of the plasma concentration-time profile in the cohorts with varying degrees of hepatic function (Cohorts 2-4).

Malnutrition is prevalent in patients with chronic liver disease, and regular meals are an important aspect for their health. CCI [REDACTED]

[REDACTED] PF-06865571 administration is planned to occur with the morning standard meal in this study to ensure consistency with the intended dosing scheme in the target patient population.

In general, participants with normal hepatic function (Cohort 1) will abstain from all concomitant treatments, except for the treatment of adverse events. Participants with impaired hepatic function (Cohorts 2, 3, and 4) are permitted to be on stable doses of background medications for the management of their concomitant medical condition(s) with some exclusions. Specifically, strong CYP3A inhibitors, strong and moderate CYP3A inducers, and time-dependent inhibitors of CYP3A are excluded from this study in participants with impaired hepatic function ^{CCI}

^{CCI} In addition, moderate CYP3A inhibitors will not be co-administered with PF-06865571 on Day 1 of this study. Similarly, BCRP substrates (eg, rosuvastatin) and sensitive CYP2C9 substrates will not be administered on Day 1 ^{CCI}

^{CCI} P-gp inhibitors (eg, digoxin) are excluded from this study. ^{CCI}

^{CCI} Participants taking metformin must not take a morning dose of metformin on Day 1 of this study.

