10. APPENDICES

Appendix 1: SAS CODE FOR ANALYSES

An example of the PROC GLM code is provided below:

```
proc glm data=tab.pk;
       class group;
       model 1&var=group/ss3 clparm alpha=0.1;
       Ismeans group;
       estimate 'Mild vs Normal'
                                          group -1 1 0 0;
       estimate 'Moderate vs Normal'
                                          group -1 0 1 0;
       estimate 'Severe vs Normal'
                                          group -1 0 0 1;
       ods output Estimates = est&var;
       ods output FitStatistics = fit&var;
       ods output ModelANOVA = tst&var;
       ods output OverallANOVA = overall&var;
run;
An example of the PROC REG code is provided below:
proc reg data=tab.pk;
       model l&var=&HepaticFunction/clb alpha=0.1;
       ods output ParameterEstimates = param&var;
       ods output FitStatistics = fit&var;
       ods output ANOVA = reg\&var;
run;
```

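### Does SAP 7.3 need a minimum number of evaluable values per cohort before an ANOVA ratio is reported?

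*SAP*

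**What the plan says.** SAP 7.3 (Pharmacokinetic Parameters) sets two thresholds close together. For summary tables, "statistics will be presented for a particular hepatic function group with ≥ 3 evaluable measurements". For the ANOVA, values coded NC (not calculated) are set to missing, and "analyses will not be performed for a particular parameter if more than 50% of the data are NC". The first rule is per group with a minimum count. The second is per parameter, with a percentage and no cohort.

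A further sentence in SAP 7.3 deals with estimates known to be biased, for example after vomiting. These are footnoted and "will not be included in the calculation of summary statistics or statistical analyses". They are not described as NC, so they do not count towards the 50%.

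SAP 7.2 uses a similar unqualified rule for concentrations: "summary statistics will not be presented at a particular time point if more than 50% of the data are missing". SAP 8.2 presents those summaries by hepatic function group.

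The model in SAP 8.1, SAP 8.2 and Appendix 1 is a single one-way ANOVA on the log scale over four cohorts, with three fixed contrasts against the reference cohort. Protocol 9.4.2.3 and SAP 8.2 both make it conditional on the data allowing it, without a number. Cohort 4 may be smaller than planned: "If recruitment across the sites selected proves to be prohibitive, study will dose only 4 participants in this cohort" (Protocol 4.1, Table 1, footnote b).

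**The concern.** The two thresholds seem to pull against each other. A cohort with one or two evaluable AUCinf values would have its descriptive statistics withheld, yet the contrast code would still return a ratio and 90% CI for it. A primary comparison would then stand on fewer values than the SAP requires before it prints a group mean.

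The denominator of the 50% is also open. One model over four cohorts suggests all participants; the parallel with SAP 7.2 makes a per-cohort reading tenable. The two readings can give different outputs from the same data.

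At stake is the credibility of a primary ratio, most likely for severe impairment. With n=1 the cohort contributes no residual degrees of freedom, so its interval width comes wholly from the other cohorts and its own data cannot test the equal-variance assumption. Protocol 2.3 says the study will contribute to dosing recommendations.

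**Working it through.** **Inputs.** SD of log AUCinf 0.19, about 6 per cohort (Protocol 9.2); predicted severe AUCinf ratio 2.9 (Protocol 4.3); 90% two-sided CI from a four-group ANOVA (SAP 8.1, Appendix 1); reduced Cohort 4 of 4 (Protocol 4.1).

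**The plan's own figure.** Table 2 of the protocol follows from half-width = t(0.95, df) × SD × √(χ²(0.80, df)/df) × √(1/6 + 1/6), with df = 24 − 4 = 20. For AUCinf: 1.7247 × 0.19 × 1.1189 × 0.5774 = 0.2117, so the interval at ratio 1 is exp(±0.2117) = 0.81 to 1.24. For Cmax (SD 0.17) it is 0.83 to 1.21. All eight rows reproduce, which confirms that the planned precision uses the pooled four-cohort variance.

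**What the 50% rule lets through.**

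- Over all participants: up to 12 of 24, or 11 of 22, may be NC. A severe cohort down to one value is 5/24 = 20.8% or 3/22 = 13.6% NC, so the model runs.
- Per cohort: a cohort of 6 passes with at most 3 NC, so at least 3 remain, which matches the descriptive threshold. A cohort of 4 passes with 2 (2/4 = 50%, not more than 50%).
- These counts take NC values alone. On the per-cohort reading, 3 NC plus 1 estimate excluded as biased would leave 2 of 6.

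**Interval at each n.** The other three cohorts are complete, df = 14 + n, and half-width h = t(0.95, df) × 0.19 × √(1/6 + 1/n). No tolerance factor is applied, so these are slightly narrower than Table 2 intervals. CI = 2.9 × exp(±h).

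| n | df | h | 90% CI | upper/lower = exp(2h) |
|---|---|---|---|---|
| 1 | 15 | 0.360 | 2.02 to 4.16 | 2.05 |
| 2 | 16 | 0.271 | 2.21 to 3.80 | 1.72 |
| 3 | 17 | 0.234 | 2.30 to 3.66 | 1.60 |
| 6 | 20 | 0.189 | 2.40 to 3.50 | 1.46 |

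**Coverage of the 90% CI.** Simulated with 400,000 draws per case; three cohorts have SD 0.19 and the test cohort has a multiple of it. The multiples 1.5 and 2 are assumptions; the documents give no cohort-specific SD.

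| SD multiple | n=1 | n=2 | n=3 | n=6 |
|---|---|---|---|---|
| 1 | 0.90 | 0.90 | 0.90 | 0.90 |
| 1.5 (assumed) | 0.76 | 0.79 | 0.81 | 0.86 |
| 2 (assumed) | 0.63 | 0.69 | 0.73 | 0.83 |

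Raising n from 2 to 3 gains 2 points (0.81 − 0.79) or 4 points (0.73 − 0.69). At n=3 the shortfall from 0.90 is still 9 or 17 points.

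**How likely the case is.** No NC rate is given. Cmax is read from the data and AUClast needs only quantifiable concentrations (Protocol Table 3), so the exposure is essentially AUCinf, which needs a terminal slope. Protocol 4.2 describes a relatively short half-life, and in Cohorts 2 to 4 "serial PK samples will be collected over 72 hours postdose to adequately characterize the elimination phase". Protocol 4.3 predicts a less than 2-fold rise in half-life. Participants leaving for non-safety reasons may be replaced (Protocol 4.1).

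**The case for a change.** The best argument for a change is that a stop rule does its work only if it is fixed before the data are seen. In an open-label study, a condition that depends on whether the data allow the analysis leaves a primary output to later judgement. The residual checks in SAP 8.2 do not help at n=1, because that residual is zero by construction. The remedy would cost a few sentences and reuse a threshold already in the section.

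Part of this stands. The denominator is undefined, excluded biased estimates are not counted, and a note of the evaluable n beside each ratio would be good reporting.

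The rest carries less weight. The two thresholds serve different outputs. The descriptive tables report an SD and CV estimated from one cohort alone, undefined at n=1 and almost uninformative at n=2; the contrast borrows its variance from all cohorts. A higher bar for the former is therefore not inconsistent. The low coverage figures come from unequal variances, a separate matter that also affects n=3 and n=6. A hard cutoff would also remove a valid if wide estimate, probably in the cohort that is hardest to recruit.

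The plan already offers context for a thin AUCinf ratio: the terminal-slope data are listed by group (SAP 8.2), significant deviations are reviewed before database closure (SAP 5.6.2), and AUClast and Cmax are primary endpoints alongside AUCinf (Protocol 3).

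**Conclusion.** No change to the plan is needed. The wording does permit a ratio from one value (all-participant reading) or from two of four (per-cohort reading, NC values alone), but applying it does not give a wrong result. Under the equal-variance assumption the ANOVA already makes, the interval is valid at every n, and its width declares the thin data: an upper-to-lower ratio of 2.05 at n=1 against 1.46 at n=6. SAP 4.1 and 4.2 attach no test or decision rule to it.

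What remains is missing detail in an unlikely situation, mainly for AUCinf, which analysts can settle under the plan's existing proviso by stating the denominator used and the evaluable n. Whether to print or withhold such a ratio is a point on which reasonable statisticians differ.

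This rests on two assumptions: that the cohort SDs are not grossly unequal, and that NC values are uncommon given 72-hour sampling in Cohorts 2 to 4 and the predicted half-life. If NC fell mainly on slow eliminators, the AUCinf ratio would be biased low, but the documents do not show this, and a minimum of 3 would not cure it.

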8. STATISTICAL METHODOLOGY AND STATISTICAL ANALYSES

8.1. Statistical Methods

For all outputs produced, the following ordering will be used:

Without Hepatic Impairment

Mild Hepatic Impairment

Moderate Hepatic Impairment

Severe Hepatic Impairment.

The effect of the hepatic impairment on PK parameters will be assessed by constructing 90% confidence intervals around the estimated difference between each of the Test (impaired groups) and the Reference (normal hepatic function group) using a one-way ANOVA model based on natural log transformed data.

The relationship between PK parameters and hepatic function parameters (eg, serum albumin concentration, or prothrombin time) will be determined by a linear regression model.

